7.3.3. Confounders and effect modifiers

Not applicable; this study is descriptive in nature.

^b Multiracial includes any combination of races or no race specified just multiracial indicated

7.5. Study size

Between 21DEC2021 and 30JUN2023 (Analysis #1 inclusion period), 22,234 adults without HIV started a new PrEP formulation in OPERA. The first formulation used during the study period was TAF/FTC oral (n=12,110, 54%), TDF/FTC oral (n=9,740, 44%), or CAB LA (n=384, 2%). An additional 292 individuals switched to CAB LA PrEP later during the study period, for a total of 767 people receiving CAB LA injections during the Analysis #1 inclusion period. Table 2 presents the precision estimates for proportions using a 95% confidence level, calculated using the standard confidence intervals equation $[p \pm 1.96\sqrt{(p*(1-p)/N)}]$. In both oral PrEP groups, the confidence interval width ranges from 0.01 to 0.02 for all proportions evaluated. For the CAB LA PrEP group, the confidence interval width ranges from 0.04 to 0.07 for all proportions evaluated.

Table 3. Precision estimates based on sample size and event proportions, using a 95% confidence level

PrEP formulation	Sample Size	Event Proportion	Lower Limit	Upper Limit	CI Width
CAB LA	767	0.1	0.08	0.12	0.04
	767	0.2	0.17	0.23	0.06
	767	0.3	0.27	0.33	0.06
	767	0.4	0.37	0.43	0.07
	767	0.5	0.46	0.54	0.07
	767	0.6	0.57	0.63	0.07
	767	0.7	0.67	0.73	0.06
	767	0.8	0.77	0.83	0.06
	767	0.9	0.88	0.92	0.04
TDF/FTC	9740	0.1	0.09	0.11	0.01
	9740	0.2	0.19	0.21	0.02
	9740	0.3	0.29	0.31	0.02
	9740	0.4	0.39	0.41	0.02
	9740	0.5	0.49	0.51	0.02
	9740	0.6	0.59	0.61	0.02
	9740	0.7	0.69	0.71	0.02
	9740	0.8	0.79	0.81	0.02
	9740	0.9	0.89	0.91	0.01
TAF/FTC	12110	0.1	0.09	0.11	0.01
	12110	0.2	0.19	0.21	0.01
	12110	0.3	0.29	0.31	0.02
	12110	0.4	0.39	0.41	0.02
	12110	0.5	0.49	0.51	0.02
	12110	0.6	0.59	0.61	0.02
	12110	0.7	0.69	0.71	0.02
	12110	0.8	0.79	0.81	0.01
	12110	0.9	0.89	0.91	0.01

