5. Assess HIV testing and STI screening patterns at index oral or LA PrEP initiation and within 12-months following index PrEP initiation among people who initiate a PrEP regimen
6. Describe demographic and clinical characteristics, HIV testing and diagnoses, as well as STI screening and diagnoses over a 12-month period of follow-up among people who are not on PrEP but could benefit from PrEP

Study Design

Design: Cohort study using secondary data from electronic medical records in the OPERA cohort.

Exposure groups: Oral PrEP, LA PrEP

Duration of study:

- Analysis #1: 2021 to 2023 (Obj 1-1a); 21DEC2021 to 30JUN2024 (Obj 2-6)
- Analysis #2: 2021 to 2024 (Obj 1-1a); 21DEC2021 to 30JUN2025 (Obj 2-6)

Population

(Obj 1) People in OPERA aged ≥ 18 years with ≥ 1 clinical encounter during the calendar year of interest and no evidence of prior HIV diagnosis.

(Obj 1a) People with an incident HIV diagnosis identified in Obj 1.

(Obj 2-5) People without HIV in OPERA aged ≥ 18 years who initiated any new PrEP formulation during the study period with or without prior PrEP use.

(Obj 6) People without HIV in OPERA aged ≥ 18 years who could benefit from PrEP and are not on PrEP

Variables

Exposures:

- PrEP use (never, use within ≤ 12 months before diagnosis, use > 12 months before diagnosis)
- Time-updated PrEP type (oral or LA)

Outcomes:

- Incident HIV diagnosis: New HIV diagnosis *and/or* detectable HIV RNA *and/or* positive antigen/antibody test
- PrEP coverage: Proportion of days of access to oral PrEP or proportion of days of coverage by CAB LA
- HIV testing/STI screening: frequency and type of tests performed

Data Sources

OPERA cohort, a multi-site observational database built from the complete patient health records managed in electronic health record (EHR) systems throughout the US.

Study Size

Between 21DEC2021 and 30JUN2023 (Analysis # 1 inclusion period), 22,234 adults without HIV started a new PrEP formulation in OPERA. The first formulation used during the study period was TAF/FTC oral (n=12,110, 54%), TDF/FTC oral (n=9,740, 44%), or CAB LA (n=384, 2%). An additional 292 individuals switched to CAB LA PrEP later during the study period, for a total of 767 people receiving CAB LA injections during the Analysis #1 inclusion period.

Protocol for Non-Interventional Studies PASS Studies and Non-PASS Studies (4.0) March 2024

Template Doc ID: TMF-15706807

Parent Doc ID: VQD-SOP-066694

Data Analysis

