5. RATIONALE AND BACKGROUND

In the US, the yearly number of HIV diagnoses declined on average by 2-3% between 2016 and 2019, with a total of 36,585 diagnoses in 2019. In 2020, a 17% decline in HIV diagnosis were observed, down to 30,403 diagnoses as a result of disruptions in testing services during the COVID-19 pandemic.¹ The number of new HIV diagnoses rebounded to 36,136 in 2021 and 37,981 in 2022.² Of approximately 1.2 million people in the US who could benefit from pre-exposure prophylaxis (PrEP) in 2022, it was estimated that only around 36% had received a PrEP prescription (due to limitations with the numerator and denominator, PrEP coverage reporting by the CDC has been paused for one year)^{3,4}

Oral PrEP was introduced as a form of HIV prevention when the single tablet combination of tenofovir disoproxil fumarate (TDF) and emtricitabine (FTC) was approved by the FDA on 16JUL2012. A meta-analysis of 14 clinical trials, open-label extension studies or demonstration studies found an incidence of HIV of 1.1% (95% CI: 0.6, 2.0). Compared to the non-PrEP control groups, the relative risk for incident HIV was 0.24 (95% CI: 0.11, 0.54).⁵ Of note, higher blood levels of TDF/FTC (indicating better adherence) were correlated with a lower incidence of HIV.⁵ The second oral PrEP option, a single tablet combination of tenofovir alafenamide (TAF) and FTC was approved on 30OCT2019. TAF/FTC was demonstrated to be non-inferior to TDF/FTC in men in a clinical trial.⁶ When taken as prescribed, daily oral PrEP reduces the risk of HIV diagnosis by 99% compared to placebo or those who do not use PrEP among men who have sex with men.⁷ Of note, the efficacy of oral PrEP is highly correlated with adherence.^{5,8} Cabotegravir long-acting injectable (CAB LA) PrEP was approved for the prevention of HIV by the FDA on 20DEC2021.⁹ Clinical trials have demonstrated the superior efficacy of CAB LA PrEP over daily oral TDF/FTC for HIV prevention.^{10,11} CAB LA PrEP consists of intramuscular injections given by a healthcare professional and is considered directly observed prevention.

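### The CAB LA head count in Section 7.5 and the Synopsis does not add up: 384 first users plus 292 switchers is 676, not the stated 767 on which the CAB LA rows of Table 3 rest

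*Protocol*

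**What the plan says.** Section 7.5 (Study size) reports that during the Analysis #1 inclusion period "22,234 adults without HIV started a new PrEP formulation in OPERA". It splits them by first formulation into 12,110 on TAF/FTC, 9,740 on TDF/FTC and 384 on CAB LA. It continues: "An additional 292 individuals switched to CAB LA PrEP later during the study period, for a total of 767 people receiving CAB LA injections".

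The Study Size entry of the Synopsis gives the same three index counts, the same 292 switchers and the same result: "for a total of 767 people receiving CAB LA injections during the Analysis #1 inclusion period".

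Table 3 in Section 7.5 uses 767 as the CAB LA sample size for all nine event proportions from 0.1 to 0.9. The text summarises those rows as follows: "For the CAB LA PrEP group, the confidence interval width ranges from 0.04 to 0.07 for all proportions evaluated".

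**The concern.** The sentence presents 767 as the sum of the people who began on CAB LA and the people who switched to it later, but the two components given do not produce that sum. The figures stand in running prose and are identical in two places, so a broken table or a redaction does not account for the gap.

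CAB LA is by far the smallest group, with hundreds of people against 9,740 and 12,110 in the oral groups. It therefore limits what the study can say by regimen type. Its size and precision are the substance of the study-size section. A reader cannot tell from the protocol how many CAB LA users the precision statement should rest on.

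**Working it through.** **Inputs** (Section 7.5, repeated in the Synopsis except for the Table 3 items): cohort 22,234; first formulation TAF/FTC 12,110, TDF/FTC 9,740, CAB LA 384; later switchers to CAB LA 292; stated CAB LA total 767; Table 3 formula p ± 1.96·√(p(1−p)/N).

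**1. Index split.** 12,110 + 9,740 + 384 = 22,234. This reproduces exactly.

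**2. CAB LA total.** 384 + 292 = 676. Stated: 767. Gap: 767 − 676 = 91, and 91/767 = 11.9%. This does not reproduce.

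**3. Which figure could be wrong.**
- If 767 and 384 are right, the switchers number 767 − 384 = 383, not 292.
- If 384 and 292 are right, the total is 676, not 767.
- If 767 and 292 are right, the first users number 767 − 292 = 475. The cohort would then be 12,110 + 9,740 + 475 = 22,325, which contradicts the stated 22,234. So 384 is the least likely culprit.
- If 767 includes people outside the cohort of 22,234, the numbers need not add up. No passage says this, and 767 would then be the wrong sample size for Table 3.

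**4. Whether the wording explains the gap.** The 292 is tied to the study period and the 767 to the Analysis #1 inclusion period. The study period is the longer of the two: Section 7.1 carries data to 30JUN2024, while inclusion closes on 30JUN2023. If some of the 292 switched after inclusion closed, the inclusion-period total would be below 676, so the difference in wording moves the sum further from 767. Established CAB LA users are not a plausible source of 91 people either, since Section 5 dates approval to 20DEC2021 and the window opens on 21DEC2021.

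**5. Reproducing Table 3 at N = 767.** Width = 2 × 1.96 × √(p(1−p)/N).
- p = 0.1: 3.92 × √(0.09/767) = 0.0425, printed as 0.04.
- p = 0.5: 3.92 × √(0.25/767) = 0.0708, printed as 0.07.

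All nine CAB LA rows reproduce to two decimals. The formula was applied correctly, and only N is in question.

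**6. The same formula at N = 676.**

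| p | Width, N = 767 | Width, N = 676 | Rounded, 767 → 676 |
|---|---|---|---|
| 0.1 / 0.9 | 0.0425 | 0.0452 | 0.04 → 0.05 |
| 0.2 / 0.8 | 0.0566 | 0.0603 | 0.06 → 0.06 |
| 0.3 / 0.7 | 0.0649 | 0.0691 | 0.06 → 0.07 |
| 0.4 / 0.6 | 0.0693 | 0.0739 | 0.07 → 0.07 |
| 0.5 | 0.0708 | 0.0754 | 0.07 → 0.08 |

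Every width grows by √(767/676) = 1.065, that is 6.5%. In absolute terms this is 0.003 to 0.005. The limits at p = 0.4 move from 0.37–0.43 to 0.36–0.44, and those at p = 0.6 from 0.57–0.63 to 0.56–0.64.

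**The case against.** The strongest case on the other side is that little depends on this number. Section 7.7 makes all analyses descriptive. There is no hypothesis test, power target or recruitment target. The study takes everyone in existing records who meets the criteria, the table shells leave space for the actual group sizes, and Analysis #2 adds a further year of inclusion. No eligibility rule, endpoint or estimator changes between 676 and 767. All of that stands, and it limits the severity. It does not remove the contradiction, which only the sponsor can resolve.

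Two stronger readings are tempting, and the documents support neither.

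- *A reader might infer that the stated CAB LA precision is too favourable.* That follows only if 676 is the correct sample size. If the error lies in 292 and the switchers number 383, every CAB LA row of Table 3 is right. The rounded change from 0.04–0.07 to 0.05–0.08 also looks larger than the real one, which is at most 0.005.
- *A reader might infer that the Table 3 formula breaks down for HIV diagnosis, with negative lower limits at around 1%.* It does not at the figure in Section 5, which is 1.1% from a meta-analysis of oral PrEP. There the interval is 0.0036 to 0.0184 for N = 767 and 0.0031 to 0.0189 for N = 676. The lower limit turns negative only when p < 1.96²/(N + 1.96²), that is below 3.8416/770.8416 = 0.0050 for N = 767 or 3.8416/679.8416 = 0.0057 for N = 676. The protocol gives no HIV incidence figure for CAB LA that would place it there. The rate of HIV diagnosis is in any case to be estimated by Poisson regression (Section 7.7.1.1), not by the Table 3 formula.

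It is fair to note that Table 3 starts at 0.1 and so says little about a rare endpoint. The protocol makes no claim about precision for HIV diagnosis that could be wrong, so adding such rows is an enhancement and not a correction.

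**Conclusion.** The contradiction is certain: 384 + 292 = 676, against a stated 767, in both the Synopsis and Section 7.5. The error lies in 292 or in 767, or 767 counts people outside the stated cohort. Ruling out 384 rests on the index split adding exactly to 22,234.

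The consequence for precision is conditional. With N = 676, CAB LA widths are 0.0452 to 0.0754 instead of 0.0425 to 0.0708, and the published range is wrong at both ends after rounding. With 383 switchers, nothing in Table 3 changes. Severity is minor to moderate: this is the sample-size figure for the limiting group, but the largest possible effect shown here is a 6.5% wider interval in a descriptive study.

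**What to change.** Re-run the CAB LA count for the Analysis #1 inclusion period and correct 292 or 767 in both the Synopsis and Section 7.5, so that first users plus switchers equals the total. If 767 was meant to include people outside the cohort of 22,234, say so and use the cohort count in Table 3.

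- If the CAB LA sample size is 676, restate the nine CAB LA rows of Table 3 and change the width range in the text to 0.05 to 0.08.
- If the switcher count is 383, leave Table 3 as it is.

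The same edit can correct the cross-reference in Section 7.5, which calls the precision table Table 2 although it is labelled Table 3. Rows at low proportions relevant to HIV diagnosis, with exact limits, may be added if the sponsor finds them useful.

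The cost is one data query and a short text edit, plus a recalculated block of nine rows if the sample size changes. No design element or analysis is affected.

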7.6. Data management

EHR data from participating clinics are encrypted, extracted and processed daily. High levels of encryption are employed to ensure the security and confidentiality of protected health information (PHI). Data are deidentified for inclusion in the OPERA database.

7.7. Data analysis

All analyses conducted for this study will be descriptive and will aim at estimating frequencies of outcomes. Analyses to meet the study objectives will be conducted twice during the study period. Analysis #1 will include data from 01JAN2021-31DEC2023 (Obj. 1-1a) and from 21DEC2021 to 30JUN2024 (Obj 2-6). Analysis #2 will be a repeat of analysis #1 with data from 1JAN2021-31DEC2024 (Obj. 1-1a) and from 21DEC2021 to 30JUN2025 (Obj 2-6).

7.7.1. Primary analysis

7.7.1.1. Main Analytical approach

People without HIV in OPERA (Obj 1)

For each calendar year, the number and percentage of new HIV diagnoses will be reported out of all individuals receiving care at an OPERA clinic.

People with a new HIV diagnosis (Obj 1.a)

Among newly diagnosed people with HIV, PrEP use (never, use within ≤ 12 months before diagnosis, use > 12 months before diagnosis) and PrEP characteristics will be described using counts and proportions for categorical variables and median and interquartile ranges for continuous variables.

PrEP users (Obj 2-5)

(Obj 2) Baseline demographic and clinical characteristics will be described at the start of PrEP use during the study period, by regimen type (oral or LA), using median and interquartile ranges for continuous variables and counts and proportions for categorical variables.

Individuals contributing to both the oral and CAB LA PrEP groups may be included in both groups.

(Obj 3) The number, percentage, and incidence rate (per 100 person-years) of incident HIV diagnoses within 12 months of starting index PrEP and through study end will be described by route of administration (time-updated, oral or LA). The timing of HIV testing relative to PrEP start and HIV diagnosis will be described to assess to possibility of attributing HIV acquisition to the correct PrEP type. Incidence rates of HIV diagnoses (per 100 person-years) within 12 months of start and through study end will be estimated using time-updated univariate Poisson regression for each regimen type (time-updated, oral vs LA) to account for varying duration of follow-up.

(Obj 4) The percentage of days with access to oral PrEP and the percentage of days with coverage by CAB LA PrEP will be described over the first 12 months after index PrEP initiation.

(Obj 5) The frequency and rate (per 100 person-years) of HIV testing, STI screening, and STI diagnoses at index PrEP initiation and in the 12-months after index PrEP initiation.

Characteristics of the tests conducted will also be described. Frequency and type of tests

performed will be described by type of healthcare provider ordering the test and clinic type. Rates of HIV and STI tests over the first 12 months will be estimated using time-updated univariate Poisson regression for each regimen type (oral vs LA).

People who could benefit from PrEP (Obj 6)

Baseline demographic and clinical characteristics will be described at the first OPERA visit with a PrEP indication, using median and interquartile ranges for continuous variables and counts and proportions for categorical variables. The frequency and rate (per 100 person-years) of HIV testing, HIV diagnoses, STI screening, and STI diagnoses will be described at the first OPERA visit with a PrEP indication and in the 12-months after the first indication.

Characteristics of the tests conducted will also be described. Frequency and type of tests performed will be described by type of healthcare provider ordering the test and clinic type. Rates of HIV tests and diagnoses as well as STI tests and diagnoses over the first 12 months will be estimated using time-updated univariate Poisson regression

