Through study end		
HIV diagnosis, n (%)		
Months from start of PrEP type to HIV diagnosis, median (IQR)		
Negative HIV test within 2 weeks before/on start of PrEP type, n (%)		

^a Incident HIV is only counted for the PrEP type used at the time of diagnosis

Table 10 Incidence rate of HIV^a within 12 months of index and through study end among PrEP users

	Oral PrEP N=	CAB LA PrEP N=
Within 12 months of index		
HIV diagnosis, n (%)		
Person-years of follow-up		
IR per 100 py (95% CI)		
Through study end		
HIV diagnosis, n (%)		
Person-years of follow-up		
IR per 100 py (95% CI)		

^a Incident HIV is only counted for the PrEP type used at the time of diagnosis

Table 11. Oral PrEP coverage within 12 months of index among **oral** PrEP users

	Oral PrEP N=
Mean # pills prescribed (SD)	
Median # of pills prescribed (IQR)	
Mean days of follow-up on oral PrEP ^a (SD)	
Median days of follow-up on oral PrEP ^a (IQR)	
Mean % access (total pills prescribed/days of follow-up) (SD)	
Median % access (total pills prescribed/days of follow-up) (IQR)	

^a If index PrEP is oral: shortest of (a) days from index to first CAB LA injection or (b) 12 months after index; if index PrEP is CAB LA injections: shortest of (a) days from start of switch to oral PrEP to study end or (b) 12 months after index

Table 12. CAB LA PrEP coverage within 12 months of index among CAB LA PrEP users

	CAB LA PrEP N=
Mean days covered ^a (SD)	
Median days covered ^a (IQR)	
Mean days of follow-up on CAB LA PrEP ^b (SD)	
Median days of follow-up on CAB LA PrEP ^b (IQR)	
Mean % coverage (days covered/days of follow-up) (SD)	
Median % coverage (days covered/days of follow-up) (IQR)	

^b Total days between injections, up to 37 days between the first 2 injections or up to 67 days between subsequent injections

^a If index PrEP is oral: shortest of (a) days from index to first CAB LA injection or (b) 12 months after index; if index PrEP is CAB LA injections: shortest of (a) days from first CAB LA injection to study end or (b) 12 months after index

Table 13. Incidence rate of HIV testing events within 12 months of index among PrEP users^a

	Oral PrEP N=	CAB LA PrEP N=
Total # HIV testing events within 12 months of index, n		
Person-years of follow-up		
IR per 100 py (95% CI)		

^a HIV testing events are only counted for the PrEP type used at the time of diagnosis

Table 14. Frequency and type of HIV testing among PrEP users^a

	Oral PrEP N=	CAB LA PrEP N=

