HIV test within 14 days before/on day of PrEP type start, n (%)		
Test type		
RNA only, n (%)		
Quantitative RNA test, n (%)		
Qualitative RNA test, n (%)		
Ag/Ab only, n (%)		
Rapid test only, n (%)		
Both RNA and Ag/Ab, n (%)		
Quantitative RNA test, n (%)		
Qualitative RNA test, n (%)		
Both RNA and rapid test, n (%)		
RNA, Ab/Ag and rapid tests, n (%)		
Days from test to PrEP type start, median (IQR)		
Any HIV test within 12 months after PrEP type start, n (%)		
Total number of testing events ^b , N		
Test type		
RNA only, n (%)		
Quantitative RNA test, n (%)		
Qualitative RNA test, n (%)		
Ag/Ab only, n (%)		
Both RNA and Ag/Ab, n (%)		
Quantitative RNA test, n (%)		
Qualitative RNA test, n (%)		
Number of HIV testing events ^b per person, median (IQR)		
Average testing interval per person (#testing events /weeks on PrEP type), median (IQR)		
Testing on schedule (oral: every 3 months (76-104 days); CAB LA: ±14 days of each injection), n (%)		

^a Tests are only counted for the PrEP type used at the time of diagnosis

^b Multiple HIV tests on the same day count as one testing event

Table 15. Frequency and type of HIV tests among oral PrEP users, by healthcare provider type ^a

	MD or DO	Physician Assistant	Nurse Practitioner	Other/unknown
Total number of HIV testing events ^b ordered				
Test type				
RNA only, n (%)				
Quantitative RNA test, n (%)				
Qualitative RNA test, n (%)				
Ag/Ab only, n (%)				
Rapid test only, n (%)				
Both RNA and Ag/Ab, n (%)				
Quantitative RNA test, n (%)				
Qualitative RNA test, n (%)				
Both RNA and rapid test, n (%)				
RNA, Ab/Ag and rapid tests, n (%)				
Testing on schedule (≤14 days before/at start or 3 months (76-104 days) after the last test, as applicable), n (%)				

^a Assessed at the test-level

^b Multiple HIV tests on the same day count as one testing event

Table 16. Frequency and type of HIV tests among CAB LA PrEP users, by healthcare provider type^a

	MD or DO	Physician Associate	Nurse Practitioner	Other/unknown
Total number of HIV testing events ^b ordered				
Test type				
RNA only, n (%)				
Quantitative RNA test, n (%)				
Qualitative RNA test, n (%)				
Ag/Ab only, n (%)				
Rapid test only, n (%)				
Both RNA and Ag/Ab, n (%)				
Quantitative RNA test, n (%)				
Qualitative RNA test, n (%)				
Both RNA and rapid test, n (%)				
RNA, Ab/Ag and rapid tests, n (%)				
Testing on schedule (≤14 days before/at first injection or ±14 days of each subsequent injection, as applicable), n (%)				

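### Default Poisson-regression intervals suit neither sparse CAB LA HIV counts nor repeated events within a person; exact limits and a person-clustered variance would

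*Protocol*

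**What the plan says.** Section 7.7.1.1 of the protocol prescribes the rate model in three places.

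- **Objective 3** (HIV diagnoses among PrEP users): rates "will be estimated using time-updated univariate Poisson regression for each regimen type (time-updated, oral vs LA) to account for varying duration of follow-up".
- **Objective 5** (PrEP users): "Rates of HIV and STI tests over the first 12 months will be estimated using time-updated univariate Poisson regression", by regimen type. This sentence covers tests only, not STI diagnoses.
- **Objective 6** (people who could benefit from PrEP): "Rates of HIV tests and diagnoses as well as STI tests and diagnoses over the first 12 months will be estimated" by the same regression, so STI diagnoses are included here.

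The Annex 1 shells report each rate per 100 person-years with a 95% confidence interval. Table 10 does this for HIV diagnoses, separately for oral and CAB LA PrEP. The testing and STI shells sum everything a person contributes over the year; in Table 13, for example, the row is "Total # HIV testing events within 12 months of index, n". The one reduction stated is for tests on the same day: "Multiple HIV tests on the same day count as one testing event", with a matching footnote for STI screening. The protocol gives no variance estimator, interval type or rule for a zero count.

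**The concern.** HIV diagnoses and testing events behave differently, and ordinary Poisson regression has a separate weakness for each.

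- **HIV diagnoses.** Section 7.3.2 censors follow-up at diagnosis, so each person has at most one event. Table 10 credits that event only to the PrEP type in use at the time. The CAB LA group is small and its count may be zero. The usual interval is built on the log rate with standard error 1/√(events), and that does not exist at zero.
- **Tests, screening events and STI diagnoses.** One person contributes several events. The default standard error is again 1/√(total events), which is right only if per-person counts have variance equal to their mean. Scheduled testing tends to make counts more regular than Poisson. STI diagnoses summed over 11 infections tend to cluster in the same people.

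At stake are the stated precision of the CAB LA HIV rate, which is central to the study's question, and the coverage of the intervals in the testing and STI tables. If the interval method were chosen only after a zero appeared, it would be a choice made after seeing results.

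**Working it through.** **1. The plan's own precision figure.** Table 3 in Section 7.5 gives 95% interval widths of 0.04 to 0.07 for CAB LA at N = 767. The formula is 2 × 1.96 × √(p(1−p)/N).
- p = 0.1: 3.92 × √(0.09/767) = 0.0425.
- p = 0.5: 3.92 × √(0.25/767) = 0.0708.

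The figures reproduce. They concern proportions from 0.1 to 0.9, so they do not bear on a rare event or on repeated counts.

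**2. Inputs and assumptions.**
- CAB LA numbers (Section 7.5): 384 first users, and a stated total of 767. The 292 switchers give 384 + 292 = 676, not 767, so a range is used.
- Assumed person-years over the first 12 months: 384 (one year per first user) to 767 (one year per person in the stated total).
- HIV rate: the protocol gives none for CAB LA. Its only PrEP incidence is 1.1%, from a meta-analysis of oral PrEP (Section 5). Rates of 0.1, 0.3 and 1.1 per 100 person-years are assumed.
- Dispersion: not given. Variance-to-mean ratios of 2 and 0.25 are assumed.

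**3. Chance of no CAB LA HIV diagnosis.** P(0) = exp(−rate × PY/100).

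| Assumed rate per 100 PY | 767 PY | 384 PY |
|---|---|---|
| 0.1 | exp(−0.767) = 46% | exp(−0.384) = 68% |
| 0.3 | exp(−2.301) = 10% | exp(−1.152) = 32% |
| 1.1 | exp(−8.437) < 0.1% | exp(−4.224) = 1.5% |

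**4. What is left with zero events.** A CAB LA-only Poisson model stopped with a boundary error. A joint fit (60 oral events in 15,000 PY, none in 700 CAB LA PY, all illustrative) gave a log rate ratio of −21.3 with standard error 15,459, and a CAB LA interval from 0 to infinity. Other limits do exist:
- Exact upper limit, 3.689/PY: 0.48 per 100 PY at 767 and 0.96 at 384.
- Profile-likelihood upper limit, 1.92/PY: 0.25 and 0.50.

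With one event at 767 PY, the log-Wald interval is 0.018–0.926 and the exact interval 0.003–0.726.

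**5. Repeated events.** If the variance-to-mean ratio is φ, the true standard error is √φ times the default, and coverage is 2Φ(1.96/√φ) − 1.
- φ = 2: 2Φ(1.386) − 1 = 83%.
- φ = 0.25: the correct standard error is √0.25 = 0.5 of the default, so the interval is twice too wide.

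Simulation (1,000 runs per scenario, 767 and 21,850 persons) agreed. Default coverage was 0.83–0.84 at φ = 2, 0.68–0.89 across φ from 1.5 to 4, and 1.00 at φ = 0.25. A person-level robust variance gave 0.94–0.96 throughout.

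**6. Absolute size for HIV testing rates.** Assume one year each and the testing frequency cited in Section 5 (four a year for oral, six for CAB LA).
- Oral: (12,110 + 9,740) × 4 = 87,400 events. Half-width 1.96/√87,400 = 0.7%, or 0.9% at φ = 2.
- CAB LA, 767 PY: 4,602 events. Half-width 2.9%, or 4.1% at φ = 2 and 1.4% at φ = 0.25.
- CAB LA, 384 PY: 2,304 events. Half-width 4.1%, or 5.8% and 2.0%.

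**The case against.** The strongest reply is that the protocol commits to none of this. It names Poisson regression and a 95% interval but neither a Wald interval nor a model-based variance. Exact or profile limits and a clustered variance are all compatible with its text. Such detail often sits in an analysis plan, and Section 7.8 refers to analysis specifications that cover model fitting. This stands, and it is why the point is not put as a demonstrated error. What remains is that the named method, run with its defaults, gives poorer intervals than an easy alternative.

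Three stronger readings are tempting and are not supported.

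- A reader might infer that Poisson regression fails and that the CAB LA cell of Table 10 would be empty. Only the log-scale coefficient and its Wald interval break down. The rate is 0, finite upper limits exist, and the shell prints the count and person-years beside the rate. Zero is also less likely through study end and in Analysis #2: at an assumed 1,500 PY, P(0) is 22% at 0.1 and 1.1% at 0.3 per 100 PY.
- A reader might infer that the testing and STI intervals are all too narrow. The protocol gives no dispersion, and regular testing would make them too wide instead.
- A reader might infer that one method is fixed for every rate. For STI diagnoses among PrEP users (Table 27) only a shell is given; the regression is stated for STI diagnoses in Objective 6 alone.

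It is also fair to say that the effect on testing rates is small in absolute terms, and that Sections 7.3.3 and 7.7 describe a purely descriptive study. That lowers the severity. It does not remove the point, because rates with intervals are what the study delivers.

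**Conclusion.** The point holds as a better choice of interval method, at minor to moderate severity. A zero CAB LA HIV count in the 12-month analysis is plausible at low true rates and unlikely near 1.1 per 100 person-years; if it occurs, the default interval is undefined while an exact one is not. For repeated events, nominal coverage would be reached only if per-person counts happened to be Poisson, and the direction of the departure is unknown. All person-years, event rates and dispersion values behind these sizes are assumptions, apart from the oral-PrEP figure of 1.1%, which is itself borrowed for CAB LA. The rates themselves are not in question.

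**What to change.** In Section 7.7.1.1 of the protocol:

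- Report HIV diagnosis rates (Annex 1, Table 10, and Table 35 for Objective 6) as events divided by person-years, with exact Poisson 95% limits.
- Keep the Poisson rate for HIV tests, STI screening events and STI diagnoses (Tables 13, 19, 34, 39 and 43, and Table 27 if the same method is meant there), with a robust variance clustered on person.

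The cost is a sentence or two and a few lines of code. Some intervals will widen, and those for very regular testing may narrow. Agreeing this before results are seen avoids choosing the interval after a zero count appears.
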